6.3.2 Derivation or calculation of outcome variable

Symptom control rate is calculated as the proportion of patients whose symptom controlled at the Week 8, 16 and 24 visits in maintenance treatment or follow-up phase. Controlled patients are defined as patients with all items ≤ 1 in A and C category of GerdQ.

Time to first relapse is defined as after 8 weeks / 2 weeks treatment, the time to the patients first come to see the investigator because of symptom recur, and need for treatment. The on-

demand drugs in the 8 weeks treatment regimen group will be dispensed after the first relapse. The average time to first relapse in the two groups will be compared.

Symptom relief is defined as patients with no more than one day mild symptoms of GERD during the previous 7 days. Symptom relief rate is calculated as the proportion of patients whose symptom relieved after 8 weeks and 2 weeks treatment.

Unscheduled hospital visit is calculated as the number of unscheduled hospital visit in 8 weeks treatment regimen and 2 weeks treatment regimen groups.

Patient satisfaction will be measured using a 7-point scale (completely satisfied-1; very satisfied-2; quite satisfied-3; satisfied-4; dissatisfied-5; very dissatisfied-6; completely dissatisfied-7). The patient will fill out the scale at Week 8, 16 and 24 visits in maintenance treatment or follow-up period. The proportion of patients satisfied (scores 1-4) or very satisfied (scores 1-2) will be calculated.

6.4 Safety

The Principal Investigator is responsible for ensuring that all staff involved in the study is familiar with the content of this section.

6.4.1 Definition of adverse events

An adverse event is the development of an undesirable medical condition or the deterioration of a pre-existing medical condition following or during exposure to a pharmaceutical product, whether or not considered causally related to the product. An undesirable medical condition can be symptoms (eg, nausea, chest pain), signs (eg, tachycardia, enlarged liver) or the abnormal results of an investigation (eg, laboratory findings, electrocardiogram). In clinical studies, an AE can include an undesirable medical condition occurring at any time, including run-in or washout periods, even if no study treatment has been administered.

The term AE is used to include both serious and non-serious AEs. Regarding non-serious AEs, in this study only non-serious AEs leading to discontinuation of IP (DAEs) will be collected.

6.4.2 Definitions of serious adverse event

A serious adverse event is an AE occurring during any study phase (ie, run-in, treatment, washout, follow-up), that fulfils one or more of the following criteria:

- Results in death
- Is immediately life-threatening

- Requires in-patient hospitalisation or prolongation of existing hospitalisation
- Results in persistent or significant disability or incapacity
- Is a congenital abnormality or birth defect
- Is an important medical event that may jeopardise the subject or may require medical intervention to prevent one of the outcomes listed above.

For further guidance on the definition of a SAE, see [Appendix B](#) to the Clinical Study Protocol.

6.4.3 Recording of SAEs/ DAEs

Time period for collection of SAEs/ DAEs

SAEs will be captured from time of signature of informed consent. DAEs will be captured from time of first dose of IP, throughout the treatment period and including the follow-up period in 2 weeks treatment regimen group.

Follow-up of unresolved SAEs/ DAEs

Any SAEs and DAEs that are unresolved at the subject's last AE assessment in the study are followed up by the investigator for as long as medically indicated, but without further recording in the CRF. AstraZeneca retains the right to request additional information for any subject with ongoing SAEs/DAEs at the end of the study, if judged necessary.

Variables

The following variables will be collect for each SAE and DAE;

- AE (verbatim)
- The date when the AE started and stopped
- Maximum intensity (mild, moderate, severe) or changes in intensity
- Whether the AE is serious or not
- Investigator causality rating against the Investigational Product (yes or no)
- Action taken with regard to investigational product
- AE caused subject's withdrawal from study (yes or no)

- Outcome.

In addition, the following variables will be collected for SAEs:

- Date AE met criteria for serious AE
- Date Investigator became aware of serious AE
- AE is serious due to
- Date of hospitalisation
- Date of discharge
- Probable cause of death
- Date of death
- Autopsy performed
- Causality assessment in relation to Study procedure(s)
- Causality assessment in relation to Other medication

Causality collection

The Investigator will assess causal relationship between Investigational Product and each Adverse Event, and answer 'yes' or 'no' to the question 'Do you consider that there is a reasonable possibility that the event may have been caused by the investigational product?'

For SAEs causal relationship will also be assessed for other medication and study procedures. Note that for SAEs that could be associated with any study procedure the causal relationship is implied as 'yes'.

A guide to the interpretation of the causality question is found in [Appendix B](#) to the Clinical Study Protocol.

SAEs/ DAEs based on signs and symptoms

All SAEs and DAEs spontaneously reported by the subject or reported in response to the open question from the study personnel: 'Have you had any health problems since the previous visit/you were last asked?', or revealed by observation will be collected and recorded in the CRF. When collecting AEs, the recording of diagnoses is preferred (when possible) to recording a list of signs and symptoms. However, if a diagnosis is known and

there are other signs or symptoms that are not generally part of the diagnosis, the diagnosis and each sign or symptom will be recorded separately.

6.4.4 Reporting of serious adverse events

All SAEs have to be reported, whether or not considered causally related to the investigational product, or to the study procedure(s). All SAEs will be recorded in the CRF.

If any SAE occurs in the course of the study, then investigators or other site personnel inform appropriate AstraZeneca representatives within one day ie, immediately but **no later than the end of the next business day** of when he or she becomes aware of it.

The designated AstraZeneca representative works with the investigator to ensure that all the necessary information is provided to the AstraZeneca Patient Safety data entry site **within one calendar day** of initial receipt for fatal and life threatening events **and within five calendar days** of initial receipt for all other SAEs.

For fatal or life-threatening adverse events where important or relevant information is missing, active follow-up is undertaken immediately. Investigators or other site personnel inform AstraZeneca representatives of any follow-up information on a previously reported SAE within one calendar day ie, immediately but **no later than the end of the next business day** of when he or she becomes aware of it.

Investigators or other site personnel send relevant CRF modules by fax to the designated AstraZeneca representative.

7. BIOLOGICAL SAMPLING PROCEDURES

7.1 Volume of blood

The total volume of blood that will be drawn from each subject in this study is as follows:

Table 4 Volume of blood to be drawn from each subject

Assessment		Sample volume (mL)	No. of samples	Total volume (mL)
Safety	Clinical chemistry	4	1	4
	Haematology	2	1	2
Total		6	2	6

7.2 Handling, storage and destruction of biological samples

The samples will be used up or disposed of according to local laboratory standardized process after analyses.

8. ETHICAL AND REGULATORY REQUIREMENTS

8.1 Ethical conduct of the study

The study will be performed in accordance with ethical principles that have their origin in the Declaration of Helsinki and are consistent with ICH/Good Clinical Practice, applicable regulatory requirements and the AstraZeneca policy on Bioethics and Human Biological Samples.

8.2 Subject data protection

The Informed Consent Form will incorporate (or, in some cases, be accompanied by a separate document incorporating) wording that complies with relevant data protection and privacy legislation.

8.3 Ethics Review

An Ethics Committee should approve the final study protocol, including the final version of the Informed Consent Form and any other written information and/or materials to be provided to the subjects. The investigator will ensure the distribution of these documents to the applicable Ethics Committee, and to the study site staff.

The opinion of the Ethics Committee should be given in writing. The investigator should submit the written approval to AstraZeneca before enrolment of any subject into the study.

The Ethics Committee should approve all advertising used to recruit subjects for the study.

AstraZeneca should approve any modifications to the Informed Consent Form that are needed to meet local requirements.

AstraZeneca will provide Ethics Committees and Principal Investigators with safety updates/reports according to local requirements, including SUSARs (Suspected Unexpected Serious Adverse Reactions), where relevant.

8.4 Informed consent

The Principal Investigator(s) at each centre will:

- Ensure each subject is given full and adequate oral and written information about the nature, purpose, possible risk and benefit of the study
- Ensure each subject is notified that they are free to discontinue from the study at any time
- Ensure that each subject is given the opportunity to ask questions and allowed time to consider the information provided
- Ensure each subject provides signed and dated informed consent before conducting any procedure specifically for the study
- Ensure the original, signed Informed Consent Form(s) is/are stored in the Investigator's Study File
- Ensure a copy of the signed Informed Consent Form is given to the subject
- Ensure that any incentives for subjects who participate in the study as well as any provisions for subjects harmed as a consequence of study participation are described in the informed consent form that is approved by an Ethics Committee.

8.5 Changes to the protocol and informed consent form

Study procedures will not be changed without the mutual agreement of the National Coordinating Investigator and AstraZeneca.

If there are any substantial changes to the study protocol, then these changes will be documented in a study protocol amendment and where required in a new version of the study protocol (Revised Clinical Study Protocol).

The amendment should be approved by each Ethics Committee before implementation. Local requirements should be followed for revised protocols.

AstraZeneca will distribute any subsequent amendments and new versions of the protocol to each Principal Investigator(s). For distribution to Ethics Committee see Section 8.3.

If a protocol amendment requires a change to a centre's Informed Consent Form, AstraZeneca and the centre's Ethics Committee should approve the revised Informed Consent Form before the revised form is used.

If local regulations require, any administrative change will be communicated to or approved by each Ethics Committee.

8.6 Audits and inspections

Authorised representatives of AstraZeneca, a regulatory authority, or an Ethics Committee may perform audits or inspections at the centre, including source data verification. The purpose of an audit or inspection is to systematically and independently examine all study-related activities and documents, to determine whether these activities were conducted, and data were recorded, analysed, and accurately reported according to the protocol, Good Clinical Practice (GCP), guidelines of the International Conference on Harmonisation (ICH), and any applicable regulatory requirements. The investigator will contact AstraZeneca immediately if contacted by a regulatory agency about an inspection at the centre.

9. STUDY MANAGEMENT BY ASTRAZENECA

9.1 Pre-study activities

Before the first subject is entered into the study, it is necessary for a representative of AstraZeneca to visit the investigational study site to:

- Determine the adequacy of the facilities
- Determine availability of appropriate subjects for the study
- Discuss with the investigator(s) (and other personnel involved with the study) their responsibilities with regard to protocol adherence, and the responsibilities of AstraZeneca or its representatives. This will be documented in a Clinical Study Agreement between AstraZeneca and the investigator.

9.2 Training of study site personnel

Before the first subject is entered into the study, an AstraZeneca representative will review and discuss the requirements of the Clinical Study Protocol and related documents with the investigational staff and also train them in any study specific procedures and system(s) utilised.

The Principal Investigator will ensure that appropriate training relevant to the study is given to all of these staff, and that any new information relevant to the performance of this study is forwarded to the staff involved.

The Principal Investigator will maintain a record of all individuals involved in the study (medical, nursing and other staff).

9.3 Monitoring of the study

During the study, an AstraZeneca representative will have regular contacts with the study site, including visits to:

- Provide information and support to the investigator(s)
- Confirm that facilities remain acceptable
- Confirm that the investigational team is adhering to the protocol, that data are being accurately and timely recorded in the CRFs, that biological samples are handled in accordance with the Laboratory Manual and that investigational product accountability checks are being performed
- Perform source data verification (a comparison of the data in the CRFs with the subject's medical records at the hospital or practice, and other records relevant to the study) including verification of informed consent of participating subjects. This will require direct access to all original records for each subject (eg, clinic charts)
- Ensure withdrawal of informed consent to the use of the subject's biological samples is reported and biological samples are identified and disposed of/destroyed accordingly, and the action is documented, and reported to the subject.

The AstraZeneca representative will be available between visits if the investigator(s) or other staff at the centre needs information and advice about the study conduct.

9.3.1 Source data

Refer to the Clinical Study Agreement for location of source data.

9.4 Study agreements

The Principal Investigator at each/the centre should comply with all the terms, conditions, and obligations of the Clinical Study Agreement, or equivalent, for this study. In the event of any inconsistency between this Clinical Study Protocol and the Clinical Study Agreement, the terms of Clinical Study Protocol shall prevail with respect to the conduct of the study and the treatment of subjects and in all other respects, not relating to study conduct or treatment of subjects, the terms of the Clinical Study Agreement shall prevail.

Agreements between AstraZeneca and the Principal Investigator should be in place before any study-related procedures can take place, or subjects are enrolled.

9.4.1 Archiving of study documents

The Investigator follows the principles outlined in the Clinical Study Agreement (CSA).

9.5 Study timetable and end of study

The end of the study is defined as ‘the last visit of the last subject undergoing the study’.

The study may be terminated at individual centres if the study procedures are not being performed according to GCP, or if recruitment is slow. AstraZeneca may also terminate the entire study prematurely if concerns for safety arise within this study or in any other study with esomeprazole.

10. DATA MANAGEMENT BY ASTRAZENECA

Data management will be performed by AstraZeneca Data Management Centre staff.

When the completed paper Case Report Forms have been scanned and indexed, the data are entered into the study database and proofread.

Adverse events and medical/surgical history will be classified according to the terminology of the latest version the Medical Dictionary for Regulatory Activities (MedDRA). Medications will be classified according to the AstraZeneca Drug Dictionary. All coding will be performed by the Medical Coding Team at the AstraZeneca Data Management Centre.

Data queries will be raised for inconsistent, impossible or missing data. All entries to the study database will be available in an audit trail.

The data will be validated as defined in the Data Management Plan. Quality control procedures will be applied to each stage of data handling to ensure that all data are reliable and have been processed correctly.

When all data have been coded, validated, signed and locked, clean file will be declared. Any treatment revealing data may thereafter be added and the final database will be locked.

11. EVALUATION AND CALCULATION OF VARIABLES BY ASTRAZENECA

11.1 Calculation or derivation of efficacy variable(s)

The calculation or derivation of efficacy variable(s) is described in section [6.3.2](#).

12. STATISTICAL METHODS AND SAMPLE SIZE DETERMINATION BY ASTRAZENECA

12.1 Description of analysis sets

Efficacy endpoints will be analyzed by randomized treatment and safety endpoints will be analyzed by the actual treatment received. MITT population will be used as the primary analysis population to observe the symptom control rate in 8 weeks treatment regimen group, compared with 2 weeks treatment regimen group after 24 weeks maintenance treatment/ follow up.

12.1.1 Efficacy analysis set

Analysis on efficacy endpoints will be performed for intention to treat (ITT) population and modified intention to treat (MITT) population. ITT is defined as all randomized subjects who have taken at least one dose of trial treatment. MITT is defined as patients in ITT population whose symptoms relieved after 8 weeks or 2 weeks esomeprazole treatment. Efficacy analysis will also be repeated in per protocol (PP) population defined as all ITT subjects without significant protocol violations/deviations. Detailed criteria and identification of the Per Protocol population will be decided in the statistical analysis plan prior to database lock.

12.1.2 Safety analysis set

Analysis on safety endpoints will be performed for subjects who take at least one dose of the trial treatment and for whom post-dose data have been collected.

12.2 Methods of statistical analyses

In general, the descriptive statistics (number, mean, median, standard deviation, minimum and maximum) will be performed for continuous variables. The frequency tables (number and percentage of subjects) will be performed for categorical variables. All statistical tests will be two-sided with the 5% level of significance.

12.2.1 Analyses of efficacy endpoints

Analysis on efficacy endpoints will be performed for ITT, MITT and PP population.

Fisher's exact test will be used to assess statistical difference in symptom control rate in 8 weeks treatment regimen group, compared with 2 weeks treatment regimen group. Differences between treatment groups in the proportion of patients very satisfied (scores 1-2) and satisfied (scores 1-4) will also be analyzed using Fisher's exact test. Symptom relief after 8 weeks or 2 weeks treatment will be summarized with number and percentage of patients in each category.

The number of unscheduled hospital visit was compared between treatments using two-sample t-test. Kaplan-Meier method will be used to assess time to first relapse and a log-rank test to provide a comparison of treatment groups.

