- In the 8 weeks treatment regimen group, the symptom relief rate after 2 weeks and 8 weeks treatment (Symptoms relief are defined as no more than one day with mild symptoms of GERD during the previous 7 days).
- The number of unscheduled hospital visit in the two treatment regimen groups.
- The proportion of patients satisfied (scores 1-4) or very satisfied (scores 1-2) in the two different treatment regimen groups after 8, 16 and 24 weeks on-demand maintenance treatment/ follow up. Patient satisfaction will be measured using a 7-point scale (completely satisfied-1; very satisfied-2; quite satisfied-3; satisfied-4; dissatisfied-5; very dissatisfied-6; completely dissatisfied-7).

Safety

- Serious adverse events (SAEs), adverse events leading to discontinuation of investigational product (DAEs)

Statistical methods

Analysis on efficacy endpoints will be performed in intention to treat (ITT) population and modified intention to treat (MITT) population. ITT is defined as all randomized subjects who have taken at least one dose of trial treatment. MITT is defined as patients in ITT population whose symptoms relieved after 8 weeks or 2 weeks esomeprazole treatment. In addition, efficacy analysis will also be repeated in per protocol (PP) population. PP population is defined as all ITT subjects without significant protocol violations/deviations.

All treatment comparisons will be done at 2-sided and the nominal level of significance is 5%.

In general, the frequency tables (number and percentage of subjects) will be performed for categorical variables. The descriptive statistics (number, mean, median, standard deviation, minimum and maximum) will be performed for continuous variables. Kaplan-Meier method will be used to assess time to first relapse.

Statistical analysis of the primary endpoint will be based on Fisher's exact test using the modified intention to treat (MITT) population.

Safety endpoints will be summarized by treatment received in the safety population. No inferential statistical analysis will be done for the safety variables. Descriptive statistics for SAEs, DAEs will be performed.

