5.2.1 Procedures for randomisation

The randomization will be performed by a computer equally for the two treatment regimens. Each centre will be provided with sealed treatment code envelopes corresponding to a list of patient randomization numbers. Randomization numbers will be assigned strictly sequentially as subjects become eligible for randomization. When a subject is allocated to a specified randomization number, the corresponding code envelope will be opened to identify the allocated treatment regimen (8 weeks or 2 weeks treatment regimen).

5.3 Procedures for handling subjects incorrectly enrolled or randomised or initiated on investigational product

Subjects who fail to meet the inclusion/exclusion criteria should not, under any circumstances, be enrolled or randomised. There can be no exceptions to this rule.

Where subjects that do not meet the selection criteria are randomised in error or incorrectly started on treatment, or where subjects subsequently fail to meet the study criteria post initiation, a discussion should occur between the AstraZeneca Study Delivery Team Physician and the Investigator regarding whether to continue or discontinue the subject from treatment.

The AstraZeneca Study Delivery Team Physician is to ensure all such decisions are appropriately documented. In situations where an agreement cannot be reached, the subject should have their study therapy stopped.

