6.2 Data collection and enrolment

At enrolment, below data will be collected:

- Age, sex and race
- Standard/significant medical and surgical history
- Physical examination and vital signs
- Blood sample for standard clinical chemistry and haematology, urine sample for urinalysis
 - Clinical chemistry: AST, ALT, creatinine, BUN
 - Haematology: Haemoglobin, leukocyte and thrombocyte counts
 - Urinalysis: pH, protein, erythrocyte, leukocyte and additional urine analyses.
- Pregnancy test
- GerdQ score
- Hp infection status (diagnosed with ¹³C-urea breath test (UBT), rapid urease test or pathologic test)
- Concomitant medication

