12.3 Determination of sample size

The primary objective of this study is to compare the symptom control rate in 8 weeks treatment regimen group, and 2 weeks treatment regimen group after 24 weeks maintenance treatment/ follow-up. Since we do not have previous data for the symptom control rate in the two treatment regimens, the sample size was calculated based on clinical experience. With a total of 170 evaluable patients, 85 in the 8 weeks treatment regimen group and 85 in the 2 weeks treatment regimen group, the power would be over 80% to detect a difference of 20% in symptom control rate between two treatment groups at two-sided 0.05 significance level using Fisher exact test, assuming the symptom control rate is around 66% in 2 weeks treatment regimen group and 86% in 8 weeks treatment regimen group (based on data from BU-NEG-0005 study). Considering the PPI response rate is around 70% and drop off rate will be 20%, around 300 patients are needed to be randomised.

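### The primary Fisher's exact test runs at about 3.4% rather than 5% and gives up about 4 points of power; a small model with baseline GerdQ would recover this and perhaps a little more

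*Protocol*

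**What the plan says.** The synopsis (Statistical methods) bases the primary analysis on Fisher's "exact test using the modified intention to treat (MITT) population". Section 12.2.1 repeats the choice: Fisher's "exact test will be used to assess statistical difference in symptom control rate in 8 weeks treatment regimen group", compared with the 2-week group. The revised efficacy table in Amendment 1 (section 6.3.1) keeps Fisher's test for Week-24 control in MITT and MITT-PP, and also uses it for the added success rate in ITT and ITT-PP. None of these places names a covariate or stratum.

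Section 12.2 sets the level: "All statistical tests will be two-sided with the 5% level of significance". Section 12.3 plans on the same test. With 85 evaluable patients per group, "the power would be over 80% to detect a difference of 20% in symptom control rate between two treatment groups". The planning rates for control are "around 66% in 2 weeks treatment regimen group and 86% in 8 weeks treatment regimen group", and the calculation is made "at two-sided 0.05 significance level using Fisher exact test".

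Baseline data are available. Section 6.2 lists the GerdQ score and "Hp infection status" among the enrolment data. On centre, section 5.2.1 says: "Each centre will be provided with sealed treatment code envelopes corresponding to a list of patient randomization numbers".

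**The concern.** Fisher's test conditions on both margins of the 2x2 table. The attainable p-values are then discrete, and the rejection rate falls short of the nominal level. With about 85 patients per arm and expected counts of uncontrolled patients well above those of a sparse table, there is no small-sample reason to accept that shortfall.

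The test also makes no use of baseline severity, although every patient has a GerdQ score at entry. If that score predicts Week-24 control, a chance difference between the arms goes straight into the primary comparison, and precision that costs nothing to obtain is left unused. At stake is the chance that the trial detects the 20-point difference it was designed for.

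**Working it through.** **Inputs.** 85 per arm; control rates 0.66 and 0.86; two-sided 0.05; Fisher's test (all section 12.3). Response rate 70% and drop-off 20% (section 12.3). Ten centres (synopsis).

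**Step 1: reproduce the plan's figure.** Power is the sum over all (x, y) of Bin(x; 85, 0.86) × Bin(y; 85, 0.66), counting the tables with Fisher p ≤ 0.05. The two-sided p is the sum of the hypergeometric probabilities no larger than that of the observed table. Result: 83.8%. At 78 per arm it is already 80.2%. The stated power of over 80% is confirmed.

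**Step 2: the same enumeration for other unadjusted tests.** Pearson's chi-square rejects when |x − y|/85 divided by √[p̄(1 − p̄) × 2/85] reaches 1.96. Mid-p counts half the probability of the observed table. Size is obtained by setting both arms to a common rate.

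| Test, 85 per arm | Power | Size at 66% | Size at 76% | Size at 86% |
|---|---|---|---|---|
| Fisher | 83.8% | 3.4% | 3.4% | 3.1% |
| Mid-p Fisher | 87.0% | 4.7% | 4.7% | 4.6% |
| Pearson chi-square | 87.8% | 4.9% | 5.1% | 4.9% |

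The gap from Fisher to chi-square is 87.8 − 83.8 = 4.0 points. At a common rate of 76%, 5.0 − 3.4 = 1.6 points of the nominal level go unused. Over common rates of 50% to 90%, Fisher's size lies between 2.9% and 3.8%.

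In patients: chi-square at 77 per arm has 84.3% power, already above Fisher at 85. The difference is 8 per arm, or 16 evaluable patients. With the Protocol's allowances that is 16/(0.7 × 0.8) ≈ 29 randomised patients.

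**Step 3: what adjustment adds, under assumptions.** The Protocol gives no association of GerdQ with Week-24 control and no between-centre variation, so both were assumed. Simulation: 170 patients, 10 equal centres, marginal rates held at 66% and 86%, 5,000 runs per scenario (Monte Carlo SE about √(0.88 × 0.12/5000) = 0.5 points). Entries are power, with simulated size in brackets.

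| Assumed log-odds SD, centre / GerdQ | Chi-square | Logistic, GerdQ | Logistic, GerdQ + nine centre terms |
|---|---|---|---|
| 0 / 0 | 87.9% (4.7%) | 87.8% (4.6%) | 88.6% (5.3%) |
| 0.5 / 0.5 | 87.7% (5.2%) | 88.7% (5.0%) | 90.0% (6.3%) |
| 0.7 / 0.7 | 88.3% (4.1%) | 89.7% (3.9%) | 91.7% (4.9%) |
| 1 / 1 | 88.0% (3.9%) | 90.9% (4.0%) | 94.0% (5.7%) |

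GerdQ alone adds 0 to about 3 points over chi-square (90.9 − 88.0 = 2.9 at the strongest setting). A separate, smaller simulation of a baseline-adjusted likelihood-ratio test (84 per arm, 1,500 runs, log-odds 0.3 to 0.9 per SD) reached at most 91.2%, against 87.4% for chi-square at 84 per arm, which is 3.8 points; its simulated size ran from 4.3% to 6.0%. Together these give roughly 0 to 4 points. Centre-stratified CMH, simulated separately, gave 88% to 91%.

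**Step 4: how large a model the data can carry.** Expected uncontrolled patients: 85 × 0.34 + 85 × 0.14 = 28.9 + 11.9 ≈ 41. Regimen, GerdQ, Hp status and nine centre terms make 12 coefficients, or 41/12 ≈ 3.4 uncontrolled patients each. Regimen and GerdQ alone make two, or about 20 each. Across all scenarios run, the model with nine centre terms had a simulated size of 4.9% to 6.4%, so part of its apparent gain is not real.

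**The case against.** The best defence is that nothing here is wrong. Fisher's test is valid, it keeps the type I error below 5%, and the sample size was computed for that same test with its power claim met. Choosing a conservative test and powering the trial for it is coherent. That stands, and it limits the point to efficiency.

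Three stronger readings are tempting, and the documents support none of them.

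- A reader might infer that most of the loss comes from ignoring centre and GerdQ. The 4 points derivable from the Protocol come entirely from Fisher's conservatism. Anything beyond them rests on assumed prognostic strengths, and entry at a GerdQ score of 8 or more narrows the covariate and may weaken it.
- A reader might infer from the envelopes held at each centre that a stratification factor was dropped from the analysis. Section 5.2.1 does not state stratification or blocking by centre.
- A reader might expect adjustment to repair the primary population. MITT keeps patients relieved at Week 8 in one arm and at Week 2 in the other. Adjusting for baseline GerdQ reduces measured imbalance but cannot restore the randomised comparison. The ITT success rate added by Amendment 1 addresses that problem more directly.

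A confidence interval for the difference and supportive adjusted analyses commonly sit in an analysis plan, which is not shown here. Their absence from the Protocol is therefore not part of this point. The primary test, by contrast, is fixed in the Protocol.

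**Conclusion.** The point holds as a missed efficiency. On the Protocol's own inputs, Fisher's test spends 3.1% to 3.4% of the nominal 5% and has 83.8% power, against 87.8% for Pearson's chi-square and 87.0% for mid-p. That part is exact and needs no outside assumption beyond the planned rates and 85 evaluable patients per arm.

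The further gain from baseline GerdQ, roughly 0 to 4 points, is conditional. It assumes a log-odds effect of 0 to 1 per SD and could be nil. The planned power is met either way, so neither the sample size nor the validity of a positive result is in question.

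**What to change.** In section 12.2.1, the synopsis and the revised efficacy table of Amendment 1:

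- Make the primary analysis a logistic regression of Week-24 control on regimen and baseline GerdQ score.
- Bring in centre only through a centre-stratified CMH analysis or centres pooled by a stated rule, not through up to nine fixed centre terms.
- Report the standardised risk difference with its 95% CI.
- Keep Fisher's test as a sensitivity analysis.
- Treat the ITT success rate in the same way.

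The cost is wording; no new data and no change in sample size are needed. There are two downsides. The trial is open-label and was already running when Amendment 1 was written, so the change and any pooling rule must be fixed before database lock and without reference to outcomes by arm. And the adjusted test, unlike Fisher's, can run slightly above 5%. If the sponsor prefers no model, a mid-p or chi-square test alone recovers about 3 to 4 points.
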